12 STATISTICAL PROCEDURES

This section provides an overview of the proposed statistical methodology for the types of data representation that will be used in analyzing the research results. At the same time, the final statistical methods will be documented in terms of statistical analysis, where they will be described in more detail than in this section of the protocol. Statistical data processing (individual maps of all patients from all centers) at the end of the study will be conducted by non-case management staff participating in the study to create conditions for independent evaluation of the results obtained.

This study does not provide for intermediate data analysis.

All statistical processing is performed after completion of the clinical part.

Descriptive statistics (averages, scatter, frequency, confidence intervals) will be presented at each visit for all safety and efficiencies collected during the study.

Statistical analysis will be conducted using Statsoft STATISTICA software v.12 or higher, or any other, which will provide the solution of statistical analysis tasks.

12.1 Justification of sample size

The study will include patients with a clinically confirmed diagnosis of ARVI (ICD-10 code: J00, J02, J04, J06), who will be randomized and distributed to one of two groups in a 1:1 ratio: Group 1 - patients who will be prescribed the study product as part of complex therapy; Group 2 - patients who will be prescribed a placebo as part of complex therapy.

A similar study of the efficacy, tolerability and safety of Polyoxidonium® in children with acute respiratory infections [5] involved 98 patients (52 in the group of the study product and symptomatic therapy, 46 in the placebo group and symptomatic therapy). The duration of fever and intoxication in the group of the study product was 2.6 ± 0.2 days, in the placebo group - 3.2 ± 0.2 days. Thus, the superiority of the efficacy of the drug Polyoxidonium® over the efficacy of a placebo in relation to the duration of the period of fever and intoxication was $-0,60 [-0,68; -0.52]$ days; the upper limit of the 95% confidence interval for the difference in efficacy of the study product and placebo was -0.52 days. Data from another study, in general, confirms the indicated efficacy values: in children who received Polyoxidonium® in the complex of therapy, compared with children who received only macrolide drugs, their body temperature decreased by 1-2 days earlier, shortness of breath, coughing, wheezing in the lungs (Kuzmenko L.G. The use of Polyoxidonium® in the treatment of frequently ill children, "EFFECTIVE PHARMACOTHERAPY. Pediatrics, No. 2, 2013).

In this study, the fever duration and intoxication period were selected as the main parameter characterizing the efficacy of the therapy. Value of $\delta = -0.52$ days is considered as the margin of excellence.

Calculation of the sample size is based on the following formula:

$$n = (Z_{\alpha} + Z_{\beta})^2 \cdot \frac{2 \cdot SD^2}{(\mu_o - \mu_p - \delta)^2}$$

where, Z_{α} and Z_{β} are critical values of the normal distribution corresponding to the established error levels α and β (α - and β -errors are 0.05 and 0.2, respectively), SD - a standard deviation [25 - 28].

As a result of calculation based on the above values ($Z\alpha=1.645$, $Z\beta=0.842$, $SD=0.2$ day, $\delta=-0.52$ day, $\mu_o=2.6$ days, and $\mu_p=3.2$ days), the sampling size was obtained that ensures a statistical study power of at least 80%, equal to 78 patients in each group (156 subjects in total). Taking into account the dropout of patients at screening, it is planned to obtain Permission of the Ministry of Health of the Russian Federation to screen 210 patients, of whom 172 will be randomized.

Patients enrolled in the study will be randomized to one of two groups using Polyoxidonium® or placebo.

12.2 Description of the statistical methods to be used, including terms of each interim analysis

Given the main study purposes (efficacy and safety assessment), the main tools for the analysis will be descriptive statistics and graphical representations.

Continuous (quantitative) variables will be tabulated using such parameters of summary statistics as the amount of data, the amount of missing data, mean, standard deviation, median, Q_1 and Q_3 , minimum and maximum values.

The descriptive statistics and tables will be presented for all demographic and baseline data. Baseline demographic characteristics, medical history and examination data are the most recent data recorded before the first product use. A comparative analysis of these data will be carried out in a population of patients who have undergone all the study procedures and completed it according to the Protocol (per-protocol (PP) population). Based on the results of efficacy analysis, the comparative statistics will be presented. Comparison of quantitative indicators satisfying the conditions of normal distribution and equality of variances will be carried out by Student's t-test. Comparison of quantitative indicators not satisfying the conditions of normal distribution and equality of variances will be carried out by Mann-Whitney test. To compare the paired quantitative indicators satisfying the conditions of normal distribution and equality of variances, the paired Student's t-test will be used; for those not satisfying the conditions of normal distribution or equality of variances - the paired Wilcoxon test. A comparative analysis of qualitative variables will be carried out by Chi-square test; if more than 20% of the expected frequencies are less than 5, the exact Fisher's two-tail test will be used.

The efficacy data analysis will be carried out in a population of patients who have undergone all the study procedures and completed it according to the Protocol (PP population). The safety population will consist of all patients who have received at least one dose of the study product, for which further safety surveillance data is provided (ITT population). The safety parameters evaluated during the study include the results of patient's general condition assessment, measurements of vital signs, a general physical examination, patient's examination, a clinical blood test, and urinalysis (compared to baseline values on Visit 0).

Throughout the study the following will be recorded:

- All study product related cases of AEs and SAEs (number, severity).
- All cases of early study termination due to the development of AEs/SAEs associated with the study product administration (number, severity).
- Local adverse reactions (number, severity, connection with the product). Safety parameters will be studied descriptively for each group.

The number of AEs and patients with AEs will be summarized by treatment groups, with a distribution by systems and selected terminology. Additional generalizations will be made on the severity, as well as the connection with the study product.

Early withdrawn patients will be presented in the Patients List and summarized by the main reason for withdrawn, and by each treatment group. Indicators of physiological functions and laboratory analyzes at the baseline (Visit 0), as well as their changes from the baseline (Visit 3), will be summarized by treatment groups. In addition, the tables of changes in laboratory analyzes based on the classification of values as low, normal or high, relative to the norm limits, will be summarized and presented by treatment groups.

Not available or missing data will not be replaced.

In addition to the standard summary analysis, the Sponsor may conduct the additional analyzes, if deemed necessary.

Interim analysis An interim analysis was not planned.

Groups for analysis

Safety population and Per-Protocol Population.

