5.8 Criteria for diagnosis

Acute respiratory viral infection (ARVI) is an acute, local (in most cases) respiratory tract infection presenting with catarrhal inflammation of the upper respiratory tract and proceeding with fever, runny nose, sneezing, cough, sore throat, a violation of the general condition of different manifestations.

The patient or parents (legal representatives) may complain of acute rhinitis and / or cough and / or conjunctival hyperemia (catarrhal conjunctivitis) in combination with symptoms of rhinitis, pharyngitis. The disease usually begins acutely, often accompanied by an increase in body temperature to subfebrile values (37.5 °C — 38.0 °C). Febrile fever is more typical for influenza, adenovirus infection, and enterovirus infections. Elevated temperature in 82% of patients is reduced by the 2-3rd day of the disease; longer (up to 5-7 days) febrile is maintained during influenza and adenovirus infection [7]. An increase of fever intensity during the disease period, or appearance of severe intoxication symptoms may indicate the accession of a bacterial infection. Repeated raise of temperature after a short-term improvement often related to development of acute otitis media following the long-lasting runny nose.

Nasopharyngitis is characterized by complaints of nasal congestion, discharge from the nasal passages, nasopharynx discomfort: burning, tingling, dryness, often accumulation of mucous discharge, which in children, flowing down the posterior pharyngeal wall, can cause a productive cough. When inflammation spreads to the mucosa of auditory tubes (Eustachitis), clicking, noise and ear pain may occur, and a sense of hearing may decrease. Clinical course of nasopharyngitis has the following age features: in infants - fever, discharge from the nasal passages, sometimes - anxiety, difficulty in feeding and falling asleep. In older children, the typical manifestations are rhinitis symptoms (peak on day 3, duration up to 6-7 days), in 1 / 3-1 / 2 patients - sneezing and / or cough (peak on day 1, average duration - 6-8 days), rarely - headache (20% in the 1st and 15% - up to the 4th day) [8].

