9.2 Diagnostic Scales and Patient's Diary

During the study, the patient's condition and the therapy efficacy will be evaluated using the following parameters: 1) "Symptom Assessment Scale" (Appendix 1) - completed by the physician, 2) IMOS scale completed by the physician (Appendix 2) and also by the parent / adoptive parent (Appendix 3).

Symptom Assessment Scale completion will be conducted on Visit 0, Visit 1, Visit 2 and Visit 3. Also, on Day 5 of therapy, in the patient's diary the Symptom Assessment Scale shall be filled in; this procedure will be performed by the parent/adoptive parent. IMOS scale completion (Appendix 3) and assessment of the ongoing therapy efficacy by the patient's parent/adoptive patient (excellent, good, satisfactory, not efficient) will be held on Visit 3.

In addition, parents / adoptive parents of patients will be given a diary to record the patient's body temperature (twice a day: morning and evening), the time of taking the study product / placebo, the time and amount of taking antipyretic (paracetamol) and other drugs and their dosage and method of taking patients' complaints.

The diary and the diagnostic scales completed by the physician are the primary documentation; upon completion of the examination by the patients, they should be collected and kept together with the patient's medical record. When using electronic diaries, the data downloaded from them will be stored in the Investigator's file.

When conducting Visit 1 procedures, the Investigator must train the parents / adoptive parent to fill out a diary. At each visit, the Investigator must verify the correctness and timeliness of filling the diary with the patient's parent / adoptive parent.

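### The 80% power in section 12.1 rests on an SD of 0.2 day for fever duration, which does not fit section 5.8; at an SD of 0.43 the decision rule has about 21% power

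*Combined protocol and SAP*

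**What the plan says.** Section 12.1 takes its inputs from one earlier study, which "involved 98 patients (52 in the group of the study product and symptomatic therapy, 46 in the placebo group and symptomatic therapy". Of its result it says: "The duration of fever and intoxication in the group of the study product was 2.6 ± 0.2 days, in the placebo group - 3.2 ± 0.2 days". The ± is not labelled as an SD or a standard error, and it refers to fever and intoxication together, whereas the primary criterion in sections 7.1 and 10 is fever duration. The plan reads it as an SD and concludes that "the upper limit of the 95% confidence interval for the difference in efficacy of the study product and placebo was -0.52 days". That limit becomes the superiority margin.

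The calculation then uses SD 0.2 day, means 2.6 and 3.2, margin −0.52 and critical values 1.645 and 0.842 (the α and β "errors are 0.05 and 0.2, respectively"). It concludes that "the sampling size was obtained that ensures a statistical study power of at least 80%, equal to 78 patients in each group". The synopsis repeats this.

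Three other places bear on the SD:

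- Section 5.8, on the natural course: "Elevated temperature in 82% of patients is reduced by the 2-3rd day of the disease; longer (up to 5-7 days) febrile is maintained", the longer course being attributed to influenza and adenovirus infection. Section 8.2 excludes a positive influenza test. No adenovirus test appears in section 9.1.1 or Appendix 5.
- Section 9.2 gives parents "a diary to record the patient's body temperature (twice a day: morning and evening"; the end of fever needs two consecutive readings.
- Sections 12.3 and 12.5 set the decision rule: the upper limit of a two-sided 95% (one-sided 97.5%) interval must lie below −0.52.

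**The concern.** An SD of 0.2 day means that children aged 1 to 12, with various viruses, differ in fever duration by only a few hours. With a normal distribution and mean 3.2, 95% of placebo children would fall between 2.8 and 3.6 days. That is hard to square with a disease that has mostly settled by day 2–3 but can run to day 5–7.

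The SD matters unusually much here because the design must resolve only 0.08 day, the gap between the expected −0.60 and the margin of −0.52. No interim analysis is planned and no sample size re-estimation is described, so nothing would correct a wrong value during the trial. A product that works as assumed could well miss the criterion, and the sponsor, sites and ethics committees would have relied on a power that the design does not deliver.

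**Working it through.** **1. The plan's figure.** n = (1.645 + 0.842)² × 2 × 0.2² / 0.08² = 77.3, so 78 per arm. Power = Φ(0.08 / (0.2 × √(2/78)) − 1.645) = 80%. Both reproduce; the issue is the input.

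**2. The earlier interval.** −0.60 ± 1.96 × 0.2 × √(1/52 + 1/46) = −0.60 ± 0.079, or [−0.68; −0.52]. The printed interval follows only if ± 0.2 is read as an SD.

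**3. Against section 5.8.** A normal distribution with mean 3.2 and SD 0.2 has Φ((3.0 − 3.2)/0.2) = 16% of placebo children at or below 3.0 days and practically none beyond 4. Section 5.8 gives 82% by day 2–3.

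**4. A bound without a shape.** Assume that 82% end no later than 3.0 days and the placebo mean is 3.2. The smallest variance puts 82% at 3.0 and 18% at 3 + 0.2/0.18 = 4.11 days. The SD is then 0.2 × √(0.82/0.18) = 0.43.

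**5. The diary.** If durations are counted in half-day steps, the least spread at mean 3.2 is 60% at 3.0 and 40% at 3.5: SD = 0.5 × √(0.6 × 0.4) = 0.245. At mean 2.6 (80% at 2.5, 20% at 3.0) the minimum is exactly 0.20.

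**6. The standard-error reading.** SDs would be 0.2 × √52 = 1.44 and 0.2 × √46 = 1.36, pooled 1.40. The interval would be −0.60 ± 1.96 × √(0.2² + 0.2²) = [−1.15; −0.05].

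**7. Power at 78 per arm, true difference −0.60.** With SE = SD × √(2/78): Φ(0.08/SE − z) against −0.52, and Φ(0.60/SE − 1.96) against zero.

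| SD (day) | Where it comes from | −0.52, z 1.645 | −0.52, z 1.96 (actual rule) | Below zero, two-sided 5% |
|---|---|---|---|---|
| 0.2 | plan | 80% | 70% | >99% |
| 0.245 | half-day steps, mean 3.2 | 65% | 53% | >99% |
| 0.43 | bound in step 4 | 31% | 21% | >99% |
| 0.5 | assumption: half at day 2, half at day 3 | 26% | 17% | >99% |
| 0.77 | assumption: 82% at day 3, 18% at day 5 | 16% | 10% | >99% |
| 1.0 | assumption | 13% | 7% | 96% |
| 1.4 | ± 0.2 as standard error | 10% | 5% | 76% |

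**8. Unequal spread.** The bound in step 4 applies to the placebo mean; the table follows the plan's formula in using one SD for both arms. With 0.43 on placebo and 0.2 on active, SE = √((0.43² + 0.2²)/78) = 0.0537 and 0.08/SE = 1.49. Power is Φ(1.49 − 1.645) = 44%, or Φ(1.49 − 1.96) = 32% under the actual rule.

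**The case against.** The plan is consistent with itself: its interval, margin and sample size all follow from ± 0.2 as an SD. Section 5.8 gives no SD, so the conflict is inferred. It does not say that the remaining 18% stay febrile for 5–7 days; it gives that as an upper range for two infections, one of which is excluded, and gives no share for the other. Efficacy is analysed per protocol only (section 12.2), and children who need antibacterial drugs are withdrawn (section 9.1.3), which may remove some long fevers. All of this stands. It is why the range above 0.43 is labelled as assumption.

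The bound also depends on reading the 82% as fever ended by 3.0 days. If the cut-off were 3.2 days or later, a mean of 3.2 would no longer force any minimum. The unlabelled source, the diary steps and the possible adenovirus fevers would still leave 0.2 unsupported.

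A reader might go further in four ways that the documents do not support:

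- *± 0.2 is a standard error, so −0.52 is a misreading.* The cited study would have to show this.
- *Section 5.8 implies an SD of 0.77 or more.* That needs an invented shape for the tail.
- *Failure is near certain.* At SDs of 0.43 to 0.5 the chance of missing the bar is 79% to 83% under the actual rule; only the upper part of the range comes close to certainty.
- *Half-day rounding contributes an SD of 0.144, leaving √(0.2² − 0.144²) = 0.138 day, or 3.3 hours, for real differences.* The subtraction fails when the spread is small against the step: a normal with mean 3.2 and SD 0.138, rounded to half days, has an SD of about 0.24, not 0.20.

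Finally, printing a low power does not raise it. That is true, but 80% power under the actual rule would need 454 per arm even at SD 0.43: (1.96 + 0.842)² × 2 × 0.43² / 0.08². The sponsor should see that before relying on the criterion.

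**Conclusion.** The concern holds. The claimed power depends entirely on an SD that the protocol does not justify and that does not fit its own account of the disease. On the stated reading of section 5.8 and the plan's placebo mean, the SD is at least 0.43 in that arm. With a common SD of 0.43, power is about 31% at the plan's own critical value and 21% under the rule in sections 12.3 and 12.5. From 0.43 to 1.4 it runs from 21% down to 5% under that rule. Half-day counting alone, with no use of section 5.8, gives 53%.

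The choice between 1.645 and 1.96 is a separate matter: it lowers power to 70% at SD 0.2, but the SD lowers it much further under either value. The low power comes from the 0.08-day distance to the margin; against a difference of zero the same sample has 76% to more than 99%. Whether −0.52 itself is sound cannot be settled without the cited study.

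**What to change.** In section 12.1 and the synopsis, with the sample size unchanged:

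1. Check in the cited study whether ± 0.2 is an SD or a standard error, and say which.
2. Replace the 80% claim by the power that 78 per arm gives under the 95% confidence interval rule over a labelled SD range from 0.43 to 1.4 (about 21% down to 5%). Mark values above 0.43 as assumptions. Beside it, give the power to show a difference below zero at two-sided 5%: over 99% at SD 0.77 or less, 96% at 1.0, 76% at 1.4.
3. If ± 0.2 proves to be a standard error, the earlier interval becomes −0.60 [−1.15; −0.05]. The margin of −0.52 then has no stated basis and must be re-derived or withdrawn.

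Steps 1 and 2 cost a source check and rewording, with no extra patients or procedures, but the stated power becomes much less favourable. Step 3, if triggered, changes the primary success rule and needs an amendment under section 14.4.

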
Study population and the number of enrolled patients:
	
Patients with a clinically confirmed diagnosis of ARVI (ICD-10 code: J00, J02, J04, J06) will be randomized and assigned to one of two groups at the ratio 1:1: Group 1 - patients will receive the study product as part of complex therapy; Group 2 - patients will receive placebo as part of complex therapy.
 
Calculation of the sample size is based on the following Formula:
 $n = (Z_{\alpha} + Z_{\beta})^2 \cdot \frac{2 \cdot SD^2}{(\mu_o - \mu_p - \delta)^2}$ 
where, Z_{α} and Z_{β} are critical values of the normal distribution corresponding to the established error levels α and β (α- and β-errors are 0.05 and 0.2, respectively), SD - a standard deviation [25 - 28].
 
As a result of calculation based on the above values ($Z_{\alpha}=1.645$, $Z_{\beta}=0.842$, $SD=0.2$ day, $\delta=-0.52$ day, $\mu_o=2.6$ days, and $\mu_p=3.2$ days), the sampling size was obtained that ensures a statistical study power of at least 80%, equal to 78 patients in each group (156 subjects in total). Taking into account the possible dropout of 10% of patients, the sample size will be extended to 86 subjects in each group (172 subjects in total). Calculations were performed using the R v Statistics package. 3.4.3.
 
Taking into account the possible dropout of patients at screening, it is planned to screen 210 patients in the study, of whom 172 will be randomized.

Study sites
	
Medical Technologies Limited Liability Company. Address: [name].
 
State Budgetary Institution of Public Health of Yaroslavl region "Regional Children's Clinical Hospital". Address: [name].
 
Municipal Children's Clinic No. 4. Address: [name].
 
Kurator, Limited Liability Company. Address: [name].
 
St. Petersburg State Budgetary Institution of Public Health "Children's Municipal Hospital No. 22". Address: [name].
 
State Budgetary Institution of Public Health of Yaroslavl region "Municipal Children's Clinical Hospital No. 5". Address: [name].
 
ArsVite Northwest Limited Liability Company. Address: [name].

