	
A superiority cut-off level $\delta = -0,52$ days was chosen to evaluate the principal efficacy parameter - fever duration. The choice is based on the results of earlier studies, which evaluated fever duration in similar cohorts of patients [4, 5].
 
Therein, the following statistical hypotheses will be verified:
 
- Null-hypothesis (H_0): efficacy of the study product does not exceed the efficacy of placebo: $H_0: \mu_o \geq \mu_p + \delta$, where, μ_o and μ_p - average fever and intoxication period in the main group (μ_o) and placebo group (μ_p);- Alternative hypothesis (H_A): therapy with the study product is better than placebo therapy: $H_A: \mu_o < \mu_p + \delta$ 
A comparison of parameters between two groups of patients can be performed by calculating the 95% confidence interval for the difference between μ_o and μ_p. Efficacy of the study product is considered higher compared with the efficacy of placebo, if the upper limit of 95% confidence interval for the difference between μ_o and μ_p values is less than - (minus) 0.52 days.
 
Safety data analysis
 
Safety population will be evaluated for all types of safety analysis. Preferred terms of MEDDRA dictionary (Preferred Term) will be used for coding and presenting the Lists of adverse events and associated diseases. All adverse events in the aggregate, as well as serious adverse events, adverse events associated with the therapy, and on other significant adverse events (for example, on adverse events that led to the cancellation of study therapy) will be presented through descriptive statistics.
 
Comparison of treatment groups by the incidence of AEs will be carried by Fisher's exact test.
 
Clinical laboratory evaluations together with indication of changes from baseline will be presented through descriptive statistics for each visit. Laboratory deviations beyond normal values will be marked. Lists and summary descriptions of clinically significant hematological laboratory abnormalities will be presented.

--	---

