7.3.2 Screening and randomization

On Visit 0 (Screening), all patients who previously meet the inclusion criteria and/or the child's parents/adoptive parents receive the detailed information about the study. After signing the Patient Information Sheet with an informed consent form, each patient is assigned a unique four-digit screening number.

Screening No. structure:

• • • • 1 - serial number of the clinical center according to the permission to conduct a study issued by the Ministry of Health of the Russian Federation.

For example: 2 - number reflecting the order of priority of patients' inclusion at each specific clinical center.

In the clinical center No. 2, one out of five patient was enrolled. This study subject shall be assigned a screening number **0205**, where 02 is the center number, 05 is a serial number of the patient enrolled to the study at this clinical center. On Visit 1, all patients who meet all inclusion criteria and do not meet any non-inclusion criteria will be randomized and assigned a three-digit random number.

The distribution of patients into 2 groups in a 1:1 ratio will be conducted according to the randomization scheme of the study protocol.

The randomization scheme will be generated by a separate document and will not be attached to the Study Protocol.

Treatment groups:

Group A: Polyoxidonium[®], nasal and sublingual spray, 6 mg/ml (NPO Petrovax Pharm, LLC, Russia).

Group B: Placebo, nasal and sublingual spray (NPO Petrovax Pharm, LLC, Russia).

Randomization using the electronic system (IWRS).

Each patient will be assigned a randomization number using a special interactive system with Internet access. To gain skills in working with the system, users will be trained and will receive a user manual.

The study will use a competitive set of patients. The number of patients included on the basis of each specific clinical center is not regulated. The recruitment of patients is terminated simultaneously in all centers after randomization of the 172nd patient, whereof the study physicians will be immediately notified.

If a patient early terminates the study, **his/her randomization number will not be reused**, and the discontinued patient cannot be included in the study afterwards. For patients who early terminated the study, the Investigator shall complete the appropriate CRF section.

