12.3 Efficacy data analysis

A superiority cut-off level $\delta = -0,52$ days was chosen to evaluate the principal efficacy parameter - fever duration. The choice is based on the results of earlier studies, which evaluated fever duration in similar cohorts of patients [4, 5].

Therein, the following statistical hypotheses will be verified:

- **Null-hypothesis (H_0):** efficacy of the study product does not exceed the efficacy of placebo:

$$H_0: \mu_o \geq \mu_p + \delta,$$

where, μ_o and μ_p - average fever and intoxication period in the main group (μ_o) and placebo group (μ_p);

- **Alternative hypothesis (H_A):** therapy with the study product is better than placebo therapy:

$$H_A: \mu_o < \mu_p + \delta$$

A comparison of parameters between two groups of patients can be performed by calculating the 95% confidence interval for the difference between μ_o and μ_p . Efficacy of the study product is considered higher compared with the efficacy of placebo, if the upper limit of 95% confidence interval for the difference between μ_o and μ_p values is less than - (minus) 0.52 days.

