12.5 Applicable level of significance

The statistical hypothesis will be verified at a 5% significance level, indicating the corresponding two-sided 95% level confidence intervals (or one-sided 97.5% confidence intervals).

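### The sample size is calculated for a one-sided 5% test, but success is judged on a two-sided 95% confidence interval, so power on the plan's own inputs is about 70–75%, not 80%

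*Combined protocol and SAP*

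**What the plan says.** **Sizing.** Section 12.1 gives the error levels by saying that the α and β "errors are 0.05 and 0.2, respectively". It then uses Zα = 1.645, Zβ = 0.842, SD = 0.2 day, means of 2.6 and 3.2 days, and a margin of -0.52 day. It reports that the result "ensures a statistical study power of at least 80%, equal to 78 patients in each group". The synopsis repeats this: "the sampling size was obtained that ensures a statistical study power of at least 80%, equal to 78 patients in each group". The synopsis adds 10% for dropout, giving 86 per group and 172 in total. Section 7.3.2 makes that number final: "The recruitment of patients is terminated simultaneously in all centers after randomization of the 172nd patient".

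**Decision.** The synopsis states the success rule: "Efficacy of the study product is considered higher compared with the efficacy of placebo, if the upper limit of 95% confidence interval" lies below -0.52 day. Section 12.3 gives the same condition, that efficacy is shown "if the upper limit of 95% confidence interval for the difference between" the two means is below that value. Section 12.5 sets a 5% significance level, "indicating the corresponding two-sided 95% level confidence intervals (or one-sided 97.5% confidence intervals".

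**The concern.** A power statement applies only to the test for which it was computed. A critical value of 1.645 is that of a one-sided 5% test. Requiring the upper limit of a two-sided 95% interval to clear the margin is a one-sided 2.5% test, with critical value 1.96. The plan therefore seems to have calculated power for an easier test than the one that decides the trial.

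The 80% figure is the stated justification for enrolling 172 children in a placebo-controlled study. Ethics committees and the regulator will read it as the chance of success if the planning assumptions are right. If it belongs to a different test, the accepted risk of a missed success is larger than the 20% stated, even when every planning assumption holds.

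**Working it through.** **Inputs, all from Section 12.1 unless noted**
- SD 0.2 day
- Assumed difference 2.6 − 3.2 = −0.60 day
- Margin −0.52 day, so the distance from assumed effect to margin is 0.08 day
- Zα = 1.645, Zβ = 0.842
- Decision rule from Sections 12.3 and 12.5: critical value 1.96 on the upper side
- 86 randomized per arm, 10% dropout (synopsis); 86 × 0.9 = 77.4, so 77 to 78 evaluable

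**Step 1. Reproduce the plan's figure.**
n = (1.645 + 0.842)² × 2 × 0.2² / 0.08² = 77.3, rounded up to 78. This matches, so the sizing is for a one-sided 5% test.

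**Step 2. Same formula with the critical value of the decision rule.**
n = (1.96 + 0.842)² × 2 × 0.2² / 0.08² = 98.1, rounded up to 99. This does not match 78.

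**Step 3. Power at the planned size.**
Power = Φ(0.08 / (0.2 × √(2/n)) − critical value). The last two columns cross-check with the noncentral t distribution.

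| Evaluable per arm | 0.08 / SE | Power, 1.645 | Power, 1.96 | t, one-sided 5% | t, one-sided 2.5% |
|---|---|---|---|---|---|
| 77 | 2.482 | 79.9% | 69.9% | 79.6% | 69.4% |
| 78 | 2.498 | 80.3% | 70.5% | 80.0% | 69.9% |
| 86 | 2.623 | 83.6% | 74.6% | 83.3% | 74.2% |

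Under the 1.96 rule, 99 per arm gives 80.3% (t: 79.97%) and 100 per arm gives 80.7% (t: 80.4%).

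**Step 4. What the plan means by a 95% interval.**
Section 12.1 quotes the earlier study's difference as −0.60 with interval −0.68 to −0.52, and says that "the upper limit of the 95% confidence interval for the difference in efficacy of the study product and placebo was -0.52 days". With 52 and 46 children and SD 0.2, SE = 0.2 × √(1/52 + 1/46) = 0.0405.
- −0.60 ± 1.96 × 0.0405 = −0.679 to −0.521, which matches.
- −0.60 ± 1.645 × 0.0405 = −0.667 to −0.533, which does not.

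The interval that supplied the margin is therefore an ordinary two-sided 95% interval.

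**The case against.** The best defence is that the hypotheses in Section 12.3 are one-sided and Section 12.5 opens with a 5% significance level. Those two statements alone would give 1.645 and agree with Section 12.1. But the same sentence of Section 12.5 goes on to name the intervals, and its one-sided form is 97.5%, not 95%. A 5% level paired with a two-sided 95% interval is 2.5% on the upper side, so this reading does not rescue the 80%.

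Section 12.3 says only that the comparison can be made by confidence interval, and Section 12.2 allows a Mann-Whitney test for non-normal data. That is true, and the figures above do not cover such a switch. Still, the interval limit is the only success criterion the plan states.

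The formula is also evaluated correctly. The fault is a mismatch between sections, not a slip in computation, and it does not raise type I error. Both points stand, but neither makes the stated power true.

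The 75% end needs every randomized child to be evaluable. Efficacy is analysed per protocol (Section 12.2), missing data are not filled in (Section 12.6), and children can be excluded for low compliance (Section 9.4) or significant deviations (Section 13.3). So 75% is a ceiling, and 70% is not a floor if exclusions exceed 10%.

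Finally, the corrected figures inherit the SD of 0.2 day. As an illustration with assumed values, power at 78 per arm under the same rule would be 38% at SD 0.3, 17% at SD 0.5 and 7% at SD 1.0. Whether 0.2 day is realistic is a separate question; the mismatch holds even if it is accepted.

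**Conclusion.** The concern holds. The claimed 80% belongs to a one-sided 5% test, while the trial is decided by a one-sided 2.5% test. Power is about 70% if the planned 10% dropout occurs and about 75% if no child is lost. The chance of missing the success criterion is therefore about 25–30%, against the 20% stated. No evaluable number attainable within 172 randomized reaches 80%.

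These figures rest on the plan's own SD and effect and on a normal-theory interval.

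**What to change.** Change the wording of Section 12.1 and the synopsis as follows.

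1. Replace Zα = 1.645 with 1.96, described as one-sided 0.025, to agree with Sections 12.3 and 12.5.
2. Remove the 80% claim together with Zβ = 0.842 and β = 0.2. Left in place beside 1.96, they would make the printed formula give 99, not 78. The formula and the 78 per group then need matching edits: present 77–78 as the expected evaluable number, not as the solution for 80% power.
3. State the power for the fixed size, for example: *With 86 children randomized per arm, SD 0.2 day, a true difference of −0.60 day and a margin of −0.52 day, the probability that the upper limit of the two-sided 95% CI lies below −0.52 day is about 70% with 77–78 evaluable per arm and about 75% with 86 evaluable per arm. These figures depend on the planning inputs and a normal-theory interval.*

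Leave the success rule unchanged. Relaxing it to a one-sided 95% bound to fit the old calculation would double the one-sided type I error from 2.5% to 5%.

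The cost is protocol and SAP text only, with 172 still randomized. The stated power becomes less favourable.
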